3.1.2 Analysis Sets

Full Analysis Set: The ‘Full Analysis Set’ (FAS) includes all subjects randomized who received at least one dose of IP in the study, and have a baseline MG-ADL assessment, and at least one post-baseline observations of MG-ADL assessment. Subjects will be analyzed

according to the treatment randomized. The efficacy analysis for RCP will be based on the FAS.

Safety Analysis Set (Randomized-controlled Period): The ‘Safety Analysis Set’ includes all subjects who received any dose of IP **during the RCP**. Subjects will be analyzed according to the treatments that they actually received. The safety, **PD**, and ADA analysis for RCP will be based on the Safety Analysis Set. A subject who received any dose of inebilizumab during the RCP will be included in the inebilizumab treatment group. A subject who received placebo only during the RCP will be included in the placebo treatment group.

[figure not shown]
Open-label Analysis Set: The ‘Open-label Analysis Set’ will include all subjects who receive any dose of inebilizumab during the OLP. The efficacy and safety for OLP will be summarized based on Open-label Analysis Set.

Any inebilizumab Analysis Set: The ‘Any inebilizumab Analysis Set’ will include all subjects who receive any dose of inebilizumab during the study. The efficacy and safety for the combined RCP and OLP will be based on the Any inebilizumab Analysis Set unless otherwise specified.

Safety Follow up Analysis Set: The ‘safety Follow up Analysis Set’ will include all subjects who entered the SFP.

Pharmacokinetic Analysis Set: The ‘PK Analysis Set’ includes all subjects who receive any dose of inebilizumab during the RCP and have at least one quantifiable serum PK observation post first dose. The PK analysis will be based on the PK Analysis Set. **Subjects will be analyzed according to the treatment that they actually received.**

[figure not shown]
Per-protocol Analysis Set (PAS): The PAS includes all subjects in the FAS who are sufficiently compliant with the protocol. Major reasons to exclude subjects from the PAS analysis set are listed below:

The complete list of reasons for excluding the subjects from the PAS will be identified and documented before study unblinding. The efficacy analysis for RCP based on the PAS will be conducted for primary and key secondary endpoints as a sensitivity analysis.

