### 9.3 Analysis Sets

**Full Analysis Set:** The “Full Analysis Set” (FAS) will include all subjects randomized who received at least 1 dose of IP in the study and have baseline and at least 1 postbaseline observation. Subjects will be analyzed according to the treatment randomized. The efficacy analysis will be based on the FAS.

**Safety Analysis Set:** The “Safety Analysis Set” will include all subjects who received any dose of IP during the RCP. Subjects will be analyzed according to the treatment that they actually received. The safety and ADA analysis in the RCP will be based on the Safety Analysis Set.

**Open-label Analysis Set:** The “Open-label Analysis Set” will include all subjects who received any dose of inebilizumab during the OLP.

**Any Inebilizumab Analysis Set:** The “Any Inebilizumab Analysis Set” will include all subjects who received any dose of inebilizumab.

**Pharmacokinetic Analysis Set:** The “PK Analysis Set” will include all subjects who received IP and have at least 1 quantifiable serum PK observation post first dose. Subjects will be analyzed according to the treatment that they actually received. The PK analysis will be based on the PK Analysis Set.

**Per-protocol Analysis Set:** The “Per-protocol Analysis Set” (PAS) will include all subjects in the FAS who are sufficiently compliant with the protocol. Major reasons to exclude subjects from the PAS analysis set are listed below:

[REDACTED]

The protocol deviations will be reviewed and documented prior to the database lock. The efficacy analysis based on the PAS will be conducted for primary and key secondary endpoints as a sensitivity analysis.

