#### 9.4.3.1 Analyses of the proportion

The primary estimand of the proportion of subjects is defined as follows:

- Population: Subjects in the FAS.
- Variable (endpoint): responder at the timepoint of interest (ie, a subject who achieved  $\geq 3$ -point improvement from baseline in MG-ADL score at Week 26 [or Week 52] and received no rescue therapy between Day 28 and Week 26 [or Week 52] will be considered as an MG-ADL responder).
- Intercurrent events:

- Rescue therapy: no rescue therapy after Day 28 during the RCP was part of the definition of the key secondary binary endpoints. A subject will be considered as a non-responder if rescue therapy was used between Day 28 and the timepoint of interest (Week 26 or Week 52).
- Rescue therapy initiated on or before Day 28 during the RCP and treatment discontinuation will be analyzed using a treatment policy strategy. Subjects who discontinue treatment early will be asked to attend scheduled evaluations until the end of the RCP. The data collected after treatment discontinuation for reasons other than rescue therapy will be included in the analysis.
- Population-level summary: difference of the inebilizumab vs placebo groups in the proportion of the responders regardless of treatment discontinuation.

Subjects will be considered as non-responders if they discontinue from the study before the timepoint of interest (Week 26 or Week 52).

The estimate of the treatment effect estimator will be evaluated using logistic regression with covariates of treatment group, baseline antibody status (AChR-Ab+ or MuSK-Ab+), baseline steroid use, baseline MG-ADL, baseline QMG score, and the corresponding baseline score. Sensitivity analyses may also be conducted for the proportions using a Cochran-Mantel-Haenszel test controlling for baseline antibody status (AChR-Ab+ or MuSK-Ab+), baseline steroid use, and baseline disease severity.

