#### 9.4.3.3 Analyses for the time to first exacerbation

The primary estimand with a treatment policy strategy is defined by the following:

- Target population: Subjects in the FAS.
- Variable: Time in days from Day 1 (dosing) to the date of the first exacerbation by the timepoint of interest (Week 26 or Week 52).
- Intercurrent event: All data captured from Day 1 to the timepoint of interest will be used for analysis. Subjects who do not complete the timepoint of interest and who have not had an exacerbation between Day 1 and the timepoint of interest will be censored at the time of discontinuation or at the timepoint of interest, whichever is earlier.
- Population-level summary: Hazard ratio between inebilizumab versus placebo.

The hazard rate in the inebilizumab group will be compared to that in the placebo group using a Cox proportional hazard model with covariates of treatment group, baseline antibody status (AChR-Ab+ or MuSK-Ab+), baseline steroid use status, baseline QMG score, and baseline MG-ADL score.

Details of the analyses will be prespecified in the SAP.

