3.4.5.2 Other Secondary Efficacy Analyses

Analyses for the proportions

The primary estimand of the proportions of subjects is defined as follows:

- Population: Subjects in the FAS.
- Variable (endpoint): responder at Week 26 or at Week 52, where a responder is defined as a subject who meets all the criteria listed in the corresponding endpoint. For example, a subject will be considered as a responder of 3-point improvement in MGADL score at Week 26 if this subject achieved (1) ≥ 3 -point improvement in MG-ADL score at Week 26 and (2) no use of rescue therapy between Day 28 and Week 26.
- Intercurrent event:

[REDACTED]

- Population-level summary: difference of the inebilizumab vs placebo groups in the proportion of the responders regardless of treatment discontinuation.

Subjects will be considered as non-responders if they discontinue from the study before the timepoint of interest (Week 26 or Week 52).

The estimate of the treatment effect estimator will be evaluated using [REDACTED] logistic regression [REDACTED]

[REDACTED]

Analyses for the changes from baseline

The primary estimand of the change from baseline is the same as the one defined for the key secondary endpoints as mentioned in Section 3.4.3.2. The estimate of the treatment effect estimator will also be based on a contrast from an MMRM approach [REDACTED]

[REDACTED]

Analyses for the time to first exacerbation

An exacerbation is defined as one of the following:

[REDACTED]

[figure not shown]
[REDACTED]

The time to first exacerbation will be analyzed utilizing treatment- policy strategy. The primary estimand of the time to first exacerbation is defined by the following:

- Target population: Subjects in the FAS
- Variable: Time in days from Day 1 to the date of the first exacerbation by the timepoint of interest (Week 26 or Week 52).
- Intercurrent event: All data captured from Day 1 to the timepoint of interest will be used for analysis. Subjects who do not complete the timepoint of interest and who don't have an exacerbation between Day 1 and the timepoint of interest will be censored at the time of discontinuation from the study or at the timepoint of interest, whichever is earlier.
- Population-level summary: Hazard ratio (HR) between inebilizumab versus placebo.

[figure not shown]
The hazard rate in the inebilizumab group will be compared to that in the placebo group using a Cox proportional hazard model [REDACTED]

[REDACTED]

[figure not shown]

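### The FAS condition of a post-baseline MG-ADL drops dosed subjects who are never scored, where the plan's own rules would count them as non-responders or keep their exacerbation events

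*SAP*

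**What the plan says.** The two documents define the Full Analysis Set differently.

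- **Protocol 9.3:** randomised subjects who "received at least 1 dose of IP in the study and have baseline and at least 1 postbaseline observation". The kind of observation is not named.
- **SAP 3.1.2:** randomised, dosed subjects with a baseline MG-ADL "and at least one post-baseline observations of MG-ADL assessment".

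SAP 3.1.2 adds: "The efficacy analysis for RCP will be based on the FAS". For time to first exacerbation, SAP 3.4.5.2 repeats it: "Target population: Subjects in the FAS". The responder estimand names the same set (protocol 9.4.3.1, SAP 3.4.5.2).

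Two rules inside those analyses bear on early leavers.

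- **Responders (protocol 9.4.3.1; SAP 3.4.5.2 has the same rule):** "Subjects will be considered as non-responders if they discontinue from the study before the timepoint of interest".
- **Exacerbation (protocol 9.4.3.3):** the variable is "Time in days from Day 1 (dosing) to the date of the first exacerbation by the timepoint of interest". Event-free leavers are censored.

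Protocol 9.4.3 gives three ways to have an exacerbation: rescue therapy, myasthenic crisis, or a defined worsening on a non-ocular MG-ADL item. Only the third needs an MG-ADL score. The first scheduled post-baseline MG-ADL is Day 15 (protocol Tables 3 and 4).

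**The concern.** Membership of the FAS depends on something observed after randomisation. A dosed subject can end up with no post-baseline MG-ADL through death, loss to follow-up, withdrawal without an early discontinuation visit (EDV), or a crisis or rescue with no score ever taken. In those cases:

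- The non-responder rule, written for people who leave before the timepoint, never reaches the subject, who is missing from numerator and denominator alike.
- A crisis or rescue that meets the exacerbation definition without any MG-ADL score is not counted, although the clock starts at Day 1.

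No visible text recovers these subjects. The per-protocol set is nested in the FAS, and the imputation analyses in SAP 3.4.2.2 test the FAS-based primary analysis. The disposition list in SAP 3.3.1 has no line for FAS exclusions. Protocol 8.1 keeps exacerbations out of the adverse event data unless they involve crisis or death, so a rescue-only event would not appear there either. SAP 3.3.4 promises a separate analysis of rescue use but does not name its analysis set.

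At stake are the completeness of the responder and exacerbation results, and a possible imbalance between arms in who is left out.

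**Working it through.** **The plan's own figures.** With 115 per arm, difference 2, SD 4 and two-sided alpha 0.05 (protocol 9.2, SAP 2.3), the two-sample t-test has 96.5% power; the plan states more than 95%. With 94 per arm in AChR-Ab+ it is 92.6%, against a stated minimum of 90%. Neither figure rests on the FAS rule. Even at 110 per arm, power is 95.8%.

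**Who is excluded.** Several routes produce a score and keep a subject in:

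- the Clinical Deterioration Visit, which should precede rescue and includes MG-ADL (protocol 6.1.5.2, Table 7);
- the EDV, which includes MG-ADL but is voluntary (protocol 6.3.2, Tables 3 and 4);
- a remote visit (protocol 6.1.5.1, Table 7);
- any later scheduled visit, since subjects who stop treatment are asked to complete the RCP schedule (protocol 6.3.1).

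Only subjects with none of these are lost.

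**How many.** The documents give no dropout assumption, so this uses a range and a constant hazard over the 14 days to the first scheduled score.

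- NMOSD study (protocol 2.1.3.3): 230 - 223 = 7 non-completers by Day 197. 7 × 14/197 = 0.50 subject.
- Assumed Week 26 dropout d: hazard h = -ln(1 - d)/183; expected number = 230 × (1 - exp(-14h)). For d = 5%, 10% and 15% this gives 0.9, 1.8 and 2.8 subjects.

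These are counts before any subject is retained by an EDV.

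**Effect of one exclusion on an arm's responder rate.** Dropping one non-responder changes r/n to r/(n - 1). The shift is r/(n(n - 1)) = p/(n - 1), where p = r/n. Response rates are assumptions.

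- Overall, n = 115, p = 0.60: 69/115 = 60.0% becomes 69/114 = 60.5%, a shift of 0.5 point.
- AChR-Ab+, n = 94, p = 0.60: 0.60/93 = 0.6 point.
- MuSK-Ab+, n = 21: 13/21 = 61.9% becomes 13/20 = 65.0%, a shift of 3.1 points. With 10/21 it is 2.4 points; with 15/21 it is 3.6.

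**Effect on the overall responder difference**, assuming 60% against 40% among all 115 per arm:

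| Excluded | Difference (points) |
|---|---|
| none | 20.0 |
| 1 inebilizumab | 20.5 |
| 3 inebilizumab | 21.6 |
| 3 placebo | 18.9 |
| 3 in each arm | 20.5 |

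Over assumed rates of 50/35, 60/40 and 70/45, one to three inebilizumab exclusions raise the difference by 0.4 to 1.9 points. Three placebo exclusions lower it by 0.9 to 1.2.

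**Effect on exacerbation.** The documents give no event counts. Under an assumed 15 against 30 events, the crude rate ratio is 15/30 = 0.50. Losing one inebilizumab subject with an event gives (14/114)/(30/115) = 0.47; losing three gives (12/112)/(30/115) = 0.41. The second case needs all three excluded subjects to be in one arm and all to have had an event.

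**Effect on the MMRM.** A subject with no post-baseline score contributes no change value, whether inside the FAS or outside it.

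**The case against.** The strongest reply is that the rule bites rarely and only outside the confirmatory analyses. The primary and all five key secondary endpoints are MMRM change scores, and the responder and exacerbation endpoints are not in the testing hierarchy (protocol 9.4.5, SAP 3.8). Both affected estimands name the FAS, so the non-responder and censoring rules can be read as operating inside that set. The SAP wording can be read as the detail that protocol 9.1 says the SAP will supply. All of this stands as a limit on the size of the point. It gives no reason to keep a condition that protects nothing.

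Some stronger readings are tempting but are not supported.

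- **Anyone with a crisis, rescue or treatment stop before Day 15 leaves the efficacy analyses.** No. One post-baseline MG-ADL at any time is enough, and the event then counts from Day 1.
- **The earliest failures are removed as a class.** No. Event-free leavers would only be censored in the Cox model, and rescue on or before Day 28 is not by itself non-response (protocol 9.4.3.1).
- **Each exclusion costs 1/115, 1/94 or 1/21 of the responder rate (0.9, 1.1 or 4.8 points).** Those are ceilings, reached only if nearly everyone else in the arm responds.
- **The rule breaches the plan's intention-to-treat principle.** Protocol 9.4.1 cites that principle for treatment discontinuation, not for the analysis set. A set limited to dosed subjects also conditions on an event after randomisation.

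The SAP's intercurrent-event text for responders is blacked out. That handling was read from the protocol, and related wording in the SAP cannot be excluded.

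**Conclusion.** The point holds in a narrow form. Dosed subjects with no post-baseline MG-ADL from any visit are dropped from the responder analysis, where the plan would otherwise count them as non-responders. Any crisis or rescue they had is lost from the exacerbation analysis. The SAP definition is also narrower than the literal protocol wording.

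About 0.5 to 3 of 230 subjects are likely to be at issue. This rests on a constant dropout hazard and on either the NMOSD completion rate or an assumed 5-15% dropout. The consequence is small overall and most visible in MuSK-Ab+, with 21 per arm. A reader might infer a bias in favour of inebilizumab, but the direction depends on which arm loses subjects. A reader might also infer a threat to the primary result, but the MMRM analyses are essentially unaffected. The change is worth making because it is free and lets the plan's own rules apply to every dosed subject.

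**What to change.** In protocol 9.3 and SAP 3.1.2, delete the post-baseline condition. Define the FAS in both as every randomised subject given any IP who has a baseline MG-ADL, analysed in the assigned arm. The baseline score is already needed for eligibility (protocol 5.1, criterion 5). If the present FAS is kept for the change-score analyses, use the wider set at least for the responder and time-to-exacerbation analyses.

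State in the SAP that subjects with no post-baseline MG-ADL:

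- count as non-responders;
- enter the Cox model with their event or censoring time;
- add no change score to the MMRM.

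Add a line to the disposition table giving, by arm and antibody population, the number of subjects with no post-baseline MG-ADL.

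The cost is a short edit in each document and one table row. No new data are needed, and protocol 9.1 allows final SAP amendments before database lock.

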3.1.3 Definition of Study Day and Baseline

In general, baseline will be defined as the last non-missing valid observation prior to the first administration of IP in the corresponding study period. In cases where baseline measurements are taken on the same day as first administration of IP and no times are reported, it will be assumed that these measurements are taken prior to first administration of IP. The definition of baseline in each study period is listed in the [REDACTED] below.

3.1.4 Analysis Windows

Unless otherwise specified, analysis visit windows will be used for all visit-based assessments to map longitudinal observations to scheduled visits, since not all assessments are performed on the scheduled day. The analysis visit windows will be defined by bisecting the interval between adjacent scheduled visit days unless otherwise specified. Detailed specifications will be included in the statistical programming plan (SPP) within each study period (RCP, OLP, and SFP).

Assessments will be mapped to analysis windows using study days and the following rules will be used to select the assessment to be included in analyses:

- If more than one assessment falls within a visit window, the closest non-missing assessment to the scheduled day will be used in the analysis.
- **If more than one non-missing assessment falls on the same day, the later one will be used in the analysis.**
- If two non-missing assessment actual dates are equidistant from the target day, the later visit will be used in the analysis.

However, an unscheduled visit with the assessments listed per protocol should be performed to evaluate worsening of MG symptoms if rescue therapy is being considered per protocol. If an unscheduled visit occurred on or before the rescue therapy use in a derived visit window, the observations collected during this unscheduled visit will be selected as the observation for this visit window. For example, the derived visit window for the scheduled Day 85 is from Day 72 to Day 105, assuming 3 records (Day 83, Day 95 and Day 100) collected in this derived visit window for this scheduled Day 85 visit, and the Day 95 visit is for RT evaluation (i.e., rescue therapy starts on or right after Day 95 visit), then the observation collected on Day 95 will be used for this scheduled Day 85 visit.

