### 9.4.1 Analysis of the Primary Efficacy Endpoint

The primary endpoint is the change from baseline in MG-ADL score at Week 26 in the overall study population (ie, the AChR-Ab+ and MuSK-Ab+ populations).

For the primary analysis, the primary estimand is defined as follows:

- Population: Subjects in the FAS.
- Variable (endpoint): change from baseline in MG-ADL score at Week 26.
- Intercurrent events:
  - Rescue therapy initiated on or after Day 28 during the RCP will be analyzed using a composite strategy. The data collected on or after the initiation of the rescue therapy will be imputed using the subject's worst observation collected before initiation of the rescue therapy.
  - Rescue therapy initiated before Day 28 during the RCP and treatment discontinuation will be analyzed using a treatment policy strategy. Subjects who discontinue treatment early will be asked to attend scheduled evaluations until the end of the RCP. The data collected after treatment discontinuation for reasons other than death or rescue therapy will be included in the analysis.
- Population-level summary: Mean difference between inebilizumab and placebo.

Rationale for estimand: The occurrence of the intercurrent event of rescue therapy is informative about the effect of treatment. If a subject is administered rescue therapy after Day 28, it may be considered that the allocated treatment was not effective, and the subject was not successfully treated. Taking rescue therapy will confound treatment effect. The intercurrent event of treatment discontinuation is considered to be part of the treatments being compared, reflecting the Intention-to-treat principle.

Supplementary analysis will be performed for the primary efficacy endpoint using a treatment policy strategy to address both intercurrent events of rescue therapy and treatment discontinuation (ie, including data collected after rescue or therapy and treatment discontinuation in the analysis). Details will be specified in the SAP.

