3.4.2.2 Analyses for Primary Efficacy Endpoint

For the primary analysis, the primary estimand is defined as follows:

1. Population: Subjects in the FAS.
2. Variable (endpoint): change from baseline in MG-ADL score at Week 26.
3. Intercurrent events:

4. Population-level summary: Mean difference between inebilizumab and placebo.

Rationale for estimand: The occurrence of the intercurrent event of rescue therapy is informative about the effect of treatment. If a subject is administered rescue therapy after Day 28, it may be considered that the allocated treatment was not effective, and the subject was not successfully treated. Taking rescue therapy will confound treatment effect.

[figure not shown]
The primary endpoint will be analyzed using a mixed-effects model for repeated measures (MMRM) analysis [REDACTED]

[figure not shown]
[REDACTED] The estimate of the treatment effect estimator will be based on a contrast from this MMRM model. The variance-covariance

matrix will be assumed to be unstructured. If the procedure doesn't converge, then a compound symmetric variance-covariance matrix will be applied.

Supplementary analysis will be performed for the primary efficacy endpoint using a treatment-policy strategy to address both intercurrent events of rescue therapy and treatment discontinuation (i.e., including data collected after rescue therapy and treatment discontinuation in the analysis).

The primary analysis will be conducted using the MMRM, which is valid under the missing at random (MAR) assumption. To examine the sensitivity of the results of the primary analysis to departures from the underlying MAR assumptions, additional analyses using Partial Dropout Reason-based Multiple Imputation (Partial-DRMI) and Dropout Reason-based Multiple Imputation (DRMI) will be performed as mentioned in Section 3.4.2.3.

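### The SAP visit-window rule lets a rescue-evaluation score displace a valid Week 26 score and, for rescues shortly before Week 26, removes post-rescue data from the treatment-policy analysis

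*SAP*

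**What the plan says.** SAP 3.1.4 builds the windows from the visit schedule: "The analysis visit windows will be defined by bisecting the interval between adjacent scheduled visit days unless otherwise specified". Its default choice among several records is that "the closest non-missing assessment to the scheduled day will be used in the analysis".

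It then adds an override for rescue. The condition is: "If an unscheduled visit occurred on or before the rescue therapy use in a derived visit window". The consequence is that "the observations collected during this unscheduled visit will be selected as the observation for this visit window". In the worked example, records exist on Days 83, 95 and 100, and Day 95 is the rescue evaluation. The SAP concludes: "then the observation collected on Day 95 will be used for this scheduled Day 85 visit". Day 83, two days from target and before rescue, and Day 100, after rescue, are both set aside.

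Two other places define what the Week 26 value should be:
- Protocol 9.4.1, composite strategy for rescue from Day 28: "The data collected on or after the initiation of the rescue therapy will be imputed", using the subject's worst earlier observation. Scores obtained before rescue are left alone.
- SAP 3.4.2.2, supplementary treatment-policy analysis: "including data collected after rescue therapy and treatment discontinuation in the analysis". SAP 3.4.1 likewise defines treatment policy as using all data whatever the rescue use.

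No visible text limits the override to one estimand or exempts Week 26.

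**The concern.** The override does a different job from either estimand. Under the composite strategy, rescue should change values only from its start onwards. If the override can reach back and replace an on-time score that preceded rescue, the Week 26 variable depends on what happens to the subject up to three weeks after Week 26. This arises in the AChR-Ab+ population. MuSK-Ab+ subjects finish the RCP at Week 26, and their upper window bound is left to the statistical programming plan (SPP).

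Under treatment policy, the score wanted at Week 26 is the one observed there, rescue or not. If an earlier deterioration score from the same window takes its place, the supplementary analysis partly repeats the composite handling that it is meant to be compared with.

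A score taken when rescue is being considered will tend to be worse than the score it displaces. If the arms differ in rescue, both estimates move in favour of the arm with fewer rescues. The rule covers all visit-based assessments, so the QMG key secondary endpoints are exposed too.

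**Working it through.** **Inputs.** Scheduled days 57, 85, 126, 183 and 225 are from Protocol Table 3 (AChR-Ab+). Protocol Table 4 (MuSK-Ab+) has the same days but stops at Day 183. The Week 26 visit allowance is ±7 days. The design difference is 2 points, the SD 4, with 230 subjects randomized 1:1, 188 of them AChR-Ab+ (SAP 2.3).

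**Step 1: reproduce the SAP's window.** The SAP states that "the derived visit window for the scheduled Day 85 is from Day 72 to Day 105". Midpoints: (57 + 85)/2 = 71 and (85 + 126)/2 = 105.5. With a whole-day midpoint assigned to the earlier window, this gives Day 72 to Day 105, an exact match.

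**Step 2: apply the same rule to Week 26.** Midpoints: (126 + 183)/2 = 154.5 and (183 + 225)/2 = 204. The AChR-Ab+ window is Day 155 to Day 204: 28 days before the target and 21 after. An on-time visit falls on Days 176 to 190, so the window runs 14 to 28 days past it.

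**Step 3: run the selection rule on illustrative subjects** (changes from baseline invented for illustration).
- Scheduled visit Day 183, change -4; evaluation Day 195, change +2; rescue Day 196. The override returns +2. The closest-to-target rule and Protocol 9.4.1 give -4.
- Evaluation Day 160, change +2; rescue Day 161; scheduled visit Day 183, change -4. The override returns +2 in every analysis. Treatment policy requires -4.
- Evaluation Day 150, rescue Day 151, scheduled visit Day 183. The rescue precedes the window, so the Day 183 score is kept.
- Scheduled visit Day 183, evaluation Day 195, no rescue given. The Day 183 score is kept.

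**Step 4: size.** The documents give no rescue rates, so these are assumptions: 26-week (182-day) rescue risk of 10-20% on placebo and 5-8% on inebilizumab, spread evenly in time and continuing at that rate after Week 26; replacement score 4-6 MG-ADL points worse than the score displaced. Low case: risk difference 10% - 5% = 5%, 4 points. High case: 20% - 8% = 12%, 6 points. The shift is treated as a change in a simple Week 26 mean.
- Placebo AChR-Ab+ subjects overwritten by rescue after Day 183: 10% × 21/182 = 1.2% to 20% × 21/182 = 2.3%, that is about 1 to 2 of 94.
- Primary, within AChR-Ab+: 0.05 × 21/182 × 4 = 0.023 to 0.12 × 21/182 × 6 = 0.083 points.
- Primary, overall population, weighting by 188/230 = 0.817: 0.019 to 0.068 points.
- Treatment policy, part before Day 183 (both populations share Days 126 and 183): 0.05 × 28/182 × 4 = 0.031 to 0.12 × 28/182 × 6 = 0.111 points.
- Treatment policy, total: 0.031 + 0.019 = 0.05 to 0.111 + 0.068 = 0.18 points.
- Equal rescue rates: risk difference 0, shift 0.

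For scale, the standard error of the difference is 4 × √(2/115) = 0.53. The primary shift is 0.04 to 0.13 standard errors, or about 1% to 3% of the 2-point effect. A more extreme assumption (30% v 5%, 6 points) gives 0.25 × 21/182 × 6 × 0.817 = 0.14 (primary), and 0.25 × 28/182 × 6 + 0.14 = 0.37 (treatment policy).

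**Step 5: how much of treatment policy survives.** With rescue spread evenly, Days 28 to 154 are 127 of the 156 days from Day 28 to Day 183. About 81% of those rescues still contribute their true post-rescue Week 26 score.

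**The case against.** The strongest reply is that the text is incomplete. SAP 3.1.4 allows for exceptions and sends detailed window specifications to the SPP, and the intercurrent-event text in SAP 3.4.2.2 is blacked out. An exemption for Week 26 or for treatment policy may exist there. This stands as a limit on certainty. But the visible rule and its worked example, followed literally, give the results above.

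It is also fair to say that the size rests on unsupported inputs. Rescue under Protocol 7.2.2 is triggered by QMG or by investigator concern, not by MG-ADL. MG-ADL also looks back over seven days and may lag an acute deterioration. The 4-6 point figure is therefore only an assumption, and the direction of any shift depends on which arm has more rescue.

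Four stronger readings might be inferred and are not supported:
- That every rescue-evaluation visit displaces the scheduled score. Rescue use must follow in the same window.
- That the treatment-policy analysis loses its post-rescue Week 26 data in general, or no longer tests the rescue strategy. The loss is confined to evaluation and rescue inside the window, so the analysis is diluted, not defeated.
- That protocol and SAP treat a same-day deterioration score in opposite ways. Protocol 9.4.1 refers to initiation of rescue, and Protocol 6.1.5.2 puts the deterioration visit before rescue starts. Such a score is pre-rescue in both documents; only a program working from dates alone would misplace it.
- That bias towards inebilizumab is established. It is conditional on unequal rescue.

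**Conclusion.** The concern holds in limited form. Read as written, SAP 3.1.4 contradicts Protocol 9.4.1 for AChR-Ab+ subjects who have a valid Week 26 score and are then evaluated and rescued up to Day 204. It contradicts SAP 3.4.1 and 3.4.2.2 for subjects evaluated and rescued inside the window before their Week 26 visit. In this second case the primary analysis is little affected, because the composite strategy replaces the post-rescue score with the worst earlier one anyway.

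On the stated assumptions the overall shift is about 0.02-0.07 points for the primary analysis and 0.05-0.18 points for treatment policy. This would be unlikely to change the trial's conclusion. The reason to act is that a confirmatory variable should not depend on events after its own time point, and a supplementary analysis should use the data it says it uses. The point should be fixed before lock; it does not threaten the design or the power.

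**What to change.** Amend SAP 3.1.4 and carry the change into the SPP:
1. A rescue-evaluation visit does not displace a scheduled assessment obtained before rescue and within the protocol visit window. Rescue after the Week 26 assessment therefore leaves the Week 26 value unchanged.
2. The rescue-evaluation score enters the pool from which the worst pre-rescue observation is taken, and fills a window that has no scheduled assessment.
3. All treatment-policy analyses use the ordinary closest-to-target rule, with post-rescue records included.

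Two clarifications can go in at the same time. State that a same-day score taken before the first rescue administration counts as pre-rescue, in line with Protocol 6.1.5.2. Replace the term unscheduled visit with the protocol's Clinical Deterioration Visit, because Protocol 6.1.5.3 reserves Unscheduled Visit for activities not linked to deterioration.

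The cost is a few sentences of SAP and SPP wording and the matching program change before database lock. No new data and no protocol amendment are needed. If the SPP already contains these exemptions, citing them in SAP 3.1.4 is enough.
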